#### 4.1.1. Dose Finding and Stopping Rules

The Sponsor will make the final decision of doses for the cohorts, including recommendation to repeat a dose or opening enrollment of the subsequent cohort. The E-DMC approval of the Sponsor's recommendation to repeat a dose or opening enrollment of the subsequent cohort will be independently assessed for each of the different age groups and will be based on the safety/tolerability and concentration data.

Repeat dosing at the assessed dose level or progression to the higher dose level will not occur if:

- Mean  $C_{max}$  **CCI** ng/mL and Mean  $AUC_{24}$  **CCI** ng•h/mL, within an age band (**CCI**)

Dosing or enrollment interruption will occur if any of the following is observed:

- Death of a participant during participation in the study receiving study intervention (sisunatovir) and assessed as possibly, probably, or definitely related to study intervention (sisunatovir) by the Investigator(s) and/or Sponsor.
- Two or more SAEs in the same SOC in the study receiving study intervention (sisunatovir) assessed as possibly, probably, or definitely related to study intervention (sisunatovir) by the Investigator(s) and/or Sponsor.
- Severe nonserious AEs, considered as, at least, possibly related to study intervention (sisunatovir), in 2 participants (receiving sisunatovir), independent of within or not within the same organ class, indicating dose limiting intolerance.
- Two or more participants receiving study intervention (sisunatovir) experience the same or a similar AE that is assessed as severe in intensity and in the opinion of the E-DMC and/or Sponsor, represent an unacceptable risk to participants enrolled in the trial.
- If two or more participants receiving study intervention (sisunatovir) develop similar clinically significant laboratory, or vital sign abnormalities, in the same organ class, indicating dose limiting intolerance.

If any of the above criteria are fulfilled, restart of dosing will only be possible if agreed by the E-DMC. Should a clear non-IMP cause for any of the above be identified, the study may continue.

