#### **Ethical Considerations:**

[figure not shown]
RSV is ubiquitous and is known to infect almost all children by 2 years of age. There is an unmet need for treatment of RSV infection and current management primarily consists of supportive care. The results of previous studies of sisunatovir support the investigation of sisunatovir for the treatment of RSV infection. The purpose of this double-blind, placebo-controlled study is to establish safety, tolerability, PK and guidance for dosing of sisunatovir in a pediatric population (up to 60 months) with RSV-LRTI for further clinical development of sisunatovir in the pediatric population.

The trial-specific risks and burdens for participants include the requirement for multiple visits, with one visit of extended duration, discomforts while undergoing study assessments (eg, blood draws, nasopharyngeal swabs), and the total blood volumes required. The study also includes the neonatal population with RSV-LRTI, with similar risks and burdens as described above. Based on clinical studies with sisunatovir thus far, gastrointestinal symptoms were the most commonly reported adverse events. Nonclinical studies suggested that the potential risks for sisunatovir may include cardiovascular, gastrointestinal, and hepatobiliary system effects. The doses proposed in this study provide exposures well below the PK stopping limit No Observed Adverse Effect Levels (NOAELs). Additionally, the proposed doses are targeting steady-state exposures comparable to CCI in adults, which were found to robustly decrease viral load and alleviate RSV symptoms relative to placebo (C5241002). Taking into account the measures to minimize risk to study participants, the potential benefit to participants with RSV-LRTI and the potential risks identified in association with sisunatovir, this dose-finding study is justified by the

anticipated benefits of sisunatovir in the clinical development of sisunatovir for the pediatric population with RSV-LRTI.

There are currently no approved RSV antivirals available, and thus no active control can be proposed as comparator. The comparator for this study is participants receiving placebo. Each cohort evaluated in the study will have participants on placebo. The placebo group is required for assessing the safety, tolerability, and palatability of the study intervention. All participants (including participants receiving placebo) enrolled in the study will receive the SOC.

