## 4. STUDY DESIGN

### 4.1. Overall Design

This study is a randomized, double-blind, sponsor-open, placebo-controlled, multicenter study in RSV-infected outpatient and hospitalized neonates, infants, and children, aged 1 day up to 60 months of age with RSV-LRTI; this is a dose finding study to evaluate the PK, safety, and tolerability of sisunatovir.

CCI [REDACTED]  
[REDACTED]

- Cohorts 1 and 2:

A: CCI [REDACTED]  
[REDACTED]

B: [REDACTED]

C: [REDACTED]

D: [REDACTED]

- Cohort 3:

E: CCI [REDACTED]  
[REDACTED]

F: [REDACTED]

G: [REDACTED]

H: [REDACTED]

Although neonates are defined by the WHO as 0-27 days old [10] CCI [REDACTED]

Sisunatovir or placebo will be administered CCI in a CCI ratio, for a period of CCI [REDACTED] for all cohorts. Each cohort will enroll CCI participants in each dose group ( CCI active: CCI placebo). In case of recruitment challenges for any cohort in the study, a minimum of CCI participants will be enrolled CCI active: CCI placebo).

Sisunatovir doses expected to produce systemic steady-state exposures comparable to the CCI mg CCI adult dose will be evaluated in dosing Cohort 1. Cohorts 1A, 1B, and 1C will initiate in parallel. CCI will receive sisunatovir or placebo, expected to produce systemic steady-state exposures comparable to the CCI mg CCI in adults. The CCI [REDACTED] may be enrolled only after E-DMC review of Cohort CCI data.

Based on analysis of PK and safety data from Cohort 1, the optional Cohort 2 (2A, 2B, 2C, 2D) may be used for further dose refinement to more closely match the CCI mg dose in CCI or to gather additional data on doses used in Cohort 1. The dose for Cohort CCI will be based on Cohort CCI. Only CCI will be enrolled CCI in CCI. Dose regimens for Cohort 2 will be provided via a digital system (eg, IWRS) upon incorporation of additional data from adults (C5241006) into the PopPK model and conducting simulations. Doses in Cohort 2 will not exceed exposures found to be well tolerated in adults in Study C5241006.

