The optional Cohort 3 (3E, 3F, 3B, 3D) may be used if additional data (exposure, safety, tolerability data) for a given dose in one or more of the CCI [REDACTED] is needed. The CCI in Cohort 3 focus on those ages most susceptible CCI [REDACTED] (less than CCI). The specific dose and CCI in the optional Cohort 3 will be determined upon review of Cohorts 1 and/or 2 PK and safety data but will not exceed exposures found to be well tolerated in adults in Study C5241006. Sponsor will determine which age groups in Cohort 3 need additional exposure, safety or tolerability data for a given dose. Dose regimens for Cohort 3 will be provided via a digital system (eg, IWRS).

The Sponsor will make the final decision of doses for the cohorts, including recommendation to repeat a dose or opening enrollment of the subsequent cohort. An independent external data monitoring committee (E-DMC) will review the unblinded safety and concentration data after completion of Day CCI visit for each cohort (approximately CCI participants, CCI participants if there are recruitment challenges) to ensure the safety of participants. The E-DMC approval of Sponsor's recommendation will be independently assessed for each of the different age groups and will be based on the safety/tolerability and concentration data (ie, CCI [REDACTED] [REDACTED] [REDACTED]). In the event that there is a safety signal of concern, all randomizations must be halted by the Sponsor until the E-DMC has completed their review and has recommended that further randomization may continue. An earlier meeting of the E-DMC can be convened, as warranted, and based on the results of the E-DMC review, the E-DMC may recommend to the Sponsor that a dose of sisunatovir be terminated. If Sponsor recommends repeating the dose, an additional CCI participants receiving active drug and

PFIZER CONFIDENTIAL

**CCI** placebo may be enrolled in the same age group within the same cohort (limit once per cohort).

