#### 4.3. Justification for Dose

The current study will evaluate safety, tolerability, PK, and guidance for future dosing of sisunatovir in a broader pediatric population (1 day to 60 months of age) with RSV-LRTI for further clinical development of sisunatovir.

To investigate the effect of sisunatovir on clinical activity following RSV infection, a viral challenge clinical study in healthy adult participants was conducted where doses of 200 mg or 350 mg Q12 × 5 days were administered following inoculation of an RSV infection (C5241002). In this study, at both doses evaluated, sisunatovir robustly decreased viral load and alleviated RSV symptoms relative to placebo. While statistically significant differences were not observed between the two dose levels relative to placebo, the 350 mg dose effect was numerically larger than the 200 mg dose. Pediatric doses are expected to produce systemic steady-state exposures comparable to the adult dose of 200 mg q12h that was found to be effective in treating viral load and symptoms of RSV in the challenge study.

Additionally, sisunatovir was administered in a completed ex-US Phase 2 study (C5241003, previously REVC003) to characterize the PK profile, safety and virologic response to sisunatovir in RSV-infected hospitalized children aged 1 month -36 months. Participants 1 month to <6 months of age were administered sisunatovir up to 2.5 mg/kg q12h for 5 days. Participants 6 months to 36 months of age were administered sisunatovir up to 5.0 mg/kg q12h for 5 days. The highest dose in each age group provided mean exposures above EC90 and below the pre-specified upper exposure limit of 294 ng/mL. Overall, sisunatovir was found to be safe for infants and children ≥1 month to ≤36 months. These results support the current study to establish safety, tolerability, PK, and guidance for dosing of sisunatovir in a broader pediatric population (1 day up to 60 months) with RSV-LRTI for further clinical development of sisunatovir.

Initial pediatric dose recommendations for Cohort 1A, 1B, and 1C are based on observed concentrations in Study C5241003 with interpolation of predicted exposures, relative to

exposure of **CCI** mg **CCI** in adults. The proposed starting dose of sisunatovir for participants **CCI** is **CCI** mg/kg and for participants **CCI** is **CCI** mg/kg (see Table 4). These doses are **CCI** than those administered in **CCI**, which were well below the PK stopping limit NOAELs.

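### The numerical PK stop in Section 4.1.1 joins mean Cmax and mean AUC24 with *and*; as the PK stopping limits are described as NOAELs, exceeding either should trigger it

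*Protocol*

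**What the plan says.** Section 4.1.1 of the protocol has one PK criterion: "Repeat dosing at the assessed dose level or progression to the higher dose level will not occur if" mean Cmax (limit redacted, ng/mL) and mean AUC24 (limit redacted, ng·h/mL), within an age band. The comparison signs and the closing bracket are also redacted. That these are upper limits is inferred from the phrase PK stopping limit used elsewhere. The type of mean is not named.

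The clinical criteria that follow in the same section are introduced differently: "Dosing or enrollment interruption will occur if any of the following is observed". If a criterion is met, "restart of dosing will only be possible if agreed by the E-DMC".

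On the nature of the limits, Section 4.3 says of doses given earlier, "which were well below the PK stopping limit NOAELs". The Synopsis (Ethical Considerations) says the same of the doses proposed here. For the previous pediatric study, Section 4.3 reports mean exposures "below the pre-specified upper exposure limit of 294 ng/mL", a single concentration.

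Two other controls matter. Under Sections 4.1 and 4.1.1, E-DMC approval to repeat a dose or open the next cohort is assessed per age group on safety and concentration data. Section 4.1 also caps the optional cohorts: "Doses in Cohort 2 will not exceed exposures found to be well tolerated in adults in Study C5241006", with the same cap for Cohort 3 ("but will not exceed exposures found to be well tolerated in adults in Study C5241006"). No such cap is stated for Cohort 1.

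**The concern.** A NOAEL marks the exposure up to which no adverse effect was seen. A band whose mean passes that level on peak or on total exposure has left the supported range on that measure, and being under the limit on the other measure does not bring it back. Joined by *and*, the two limits do not act as two limits: the stop waits until the laxer one is also reached. No passage gives a reason for requiring both.

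At stake is whether the one numerical PK stop in Section 4.1.1 works when only one exposure measure is too high, in a study that enrolls children from 1 day of age.

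**Working it through.** **Logic.** Let C be the event that mean Cmax is over its limit and A the event that mean AUC24 is over its limit. The rule as written stops on C∩A; the proposed rule stops on C∪A. Since C∩A lies inside C∪A, the change cannot release any band that is stopped now. The added holds are P(C∪A) − P(C∩A), the chance that exactly one limit is exceeded.

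**No plan figure to reproduce.** The limits are redacted and the sample size is empirical, so the sizes below are illustrations.

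**Inputs from the documents.**
- Variability: the %CVs for Cmax,ss and AUCss in all three data columns of Table 4.
- Bound on active children per band: 108 / 12 bands = 9, including placebo and any repeat block. A repeat block has at least one active and one placebo child, so first enrollment is at most 7, of whom at most 6 are active.

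**Assumed.** 4 active children in a reduced band; lognormal data; log-scale correlation 0.9 between Cmax and AUC; arithmetic means; Cmax and AUC24 observed without error; true means expressed as multiples of the redacted limits.

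**Formulas.** Log-SD = √ln(1+CV²); for CV 146%, √ln(1+1.46²) = 1.068. Simulation: 400,000 samples per setting, each sample mean compared with its limit.

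*Benefit case:* true mean Cmax is 1.5 times its limit and the limits are 1.5-fold apart, so true mean AUC24 is 1.5/1.5 = 1.0 times its limit. *Cost cases:* both true means at 0.5 or at 0.8 times their limits.

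| Table 4 column | CV Cmax / AUC | log-SDs | n active | Hold, *and* → *or* | Extra holds at 0.5× | Extra holds at 0.8× |
|---|---|---|---|---|---|---|
| n=11 (heading redacted) | 146% / 121% | 1.068 / 0.950 | 4 | 37.6% → 64.1% | 5.2 points | 12.3 points |
| | | | 6 | 39.3% → 70.1% | 4.1 | 12.2 |
| 3.5 mg/kg (n=3) | 249% / 224% | 1.405 / 1.340 | 4 | 30.4% → 52.1% | 7.1 | 12.4 |
| | | | 6 | 32.6% → 57.2% | 6.6 | 12.8 |
| 5 mg/kg (n=2) | 98% / 79% | 0.820 / 0.696 | 4 | 41.7% → 75.0% | 3.0 | 11.5 |
| | | | 6 | 43.1% → 81.6% | 1.9 | 11.1 |

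Over all rows: 30-43% → 52-82%, with a cost of 2-7 points at 0.5× and 11-13 points at 0.8×.

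**How little the stricter limit does under *and*.** In the benefit case, using the AUC24 limit alone gives 38.6% in the first row, against 37.6% under *and*. Over all rows the difference is 0.1 to 2.1 points.

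**Sensitivity.**
- If the limits are aligned (both true means 1.5 times their limits), the gain is smaller, about 10-17 points over all rows.
- If the correlation is 0.8 rather than 0.9, the benefit-case gain is about 27-40 points, the cost 2-10 points at 0.5× and 15-18 at 0.8×.
- If it is 0.98, the gain is about 18-38 points, the cost 1-3 points at 0.5× and 5-6 at 0.8×.

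**Type of mean.** The arithmetic/geometric ratio is √(1+CV²). At CVs of 146% and 121% it is √(1+1.46²) = 1.77 and √(1+1.21²) = 1.57. At the same numerical limits, a geometric mean is therefore the laxer test.

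**The case against.** **The bullet mandates a stop; it does not license proceeding.** A reader might infer that a band over one limit may simply repeat or step up. The documents do not support that: E-DMC approval per age group, on concentration data, is needed first. This stands and is the main reason severity is modest. It does not correct the written rule.

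**Step-ups are largely covered elsewhere.** A reader might also infer that dose increases are unguarded. Section 6.6 bars dose changes within a cohort, so a refined dose for a Cohort 1 band comes in Cohort 2 or 3, and both are capped at exposures well tolerated in adults. This stands too. What remains is mainly one repeat block per Cohort 1 band (Section 4.1 allows one) and the Cohort 1D dose, which is set after earlier data are evaluated.

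**The supporting texts do not prove the intent.** Calling the limits NOAELs does not say whether Cmax and AUC24 are separate limits or a pair; 294 ng/mL belongs to another study; and the word *any* heads a separate list with a different action. All fair. *And* may be loose drafting for two separate limits, in which case *or* states what was meant. If both were meant to be required, the reason should be given.

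**The numbers rest on assumptions.** True. The n=11 column's population is redacted, the other two columns have 3 and 2 children, and three PK samples per child with model-based estimates may make Cmax and AUC more closely correlated than assumed. Only the direction is certain.

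**False holds are not free.** Near the limits they add 11-13 points. The protocol describes the proposed exposures as well below the limits, where the cost is smaller. Whether the restart sentence covers the PK bullet is not explicit; if it does, a false hold is a delay for E-DMC review.

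**Conclusion.** The point holds in a limited form. Read literally, the numerical PK stop in Section 4.1.1 is not triggered when only one of two limits is exceeded, which fits poorly with limits described as NOAELs. Changing the connective can only strengthen the stop. The effect on hold rates (about 30-43% to 52-82% in the benefit case) depends on assumed limits, gap between limits, sample size and correlation, and on arithmetic means. It should not be read as an estimate for this trial.

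This is a worthwhile, inexpensive safety improvement of modest severity. It does not show that children are unprotected, since the E-DMC and the adult-exposure caps remain.

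The unnamed type of mean is missing detail and not a separate fault. The SAP default for continuous data is arithmetic (Section 5.2.1), while Table 4 and Protocol Section 9.3.3 say geometric where they mean it. Nothing here supports switching to geometric means at the same limits, which would weaken the stop.

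**What to change.** In Section 4.1.1, reword the bullet to: *mean Cmax or mean AUC24 is above its limit, within an age band*. Keep both numerical limits. As a clarification in the same sentence, state the type of mean on which the limits were derived. If the E-DMC charter (not among the documents) repeats the rule, align it. It would also help to say whether the E-DMC restart sentence applies to this bullet.

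The edit is one word plus one adjective and needs no new data or change in sample size. The running cost is the additional holds of bands truly below both limits given under working.

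### The only interruption rule that pools related severe events across organ classes excludes serious ones, so a dissimilar pair can lose its trigger when one event becomes serious

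*Protocol*

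**What the plan says.** Protocol Section 4.1.1 introduces its event-based rules with "Dosing or enrollment interruption will occur if any of the following is observed". There are five, numbered here in the order listed:

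1. One related death on sisunatovir.
2. "Two or more SAEs in the same SOC in the study receiving study intervention (sisunatovir) assessed as possibly, probably, or definitely related" to the study drug. This counts events rather than children and asks for neither severe intensity nor a judgement about tolerability.
3. "Severe nonserious AEs, considered as, at least, possibly related to study intervention (sisunatovir), in 2 participants (receiving sisunatovir), independent of within or not within" one organ class. The rule ends with a further condition: "in 2 participants (receiving sisunatovir), independent of within or not within the same organ class, indicating dose limiting intolerance".
4. Two or more children on sisunatovir who "experience the same or a similar AE that is assessed as severe in intensity", where the E-DMC or the sponsor considers the risk unacceptable. Seriousness is not mentioned.
5. Two or more children on sisunatovir with similar, clinically significant laboratory or vital-sign abnormalities in one organ class, again with a judgement of dose-limiting intolerance.

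The consequence follows: "If any of the above criteria are fulfilled, restart of dosing will only be possible if agreed by the E-DMC". The next sentence lets the study continue if a clear cause other than the study drug is found.

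Section 4.1 has a separate safeguard: "In the event that there is a safety signal of concern, all randomizations must be halted by the Sponsor". That halt lasts until the E-DMC has finished its review and recommended that randomization resume. The E-DMC can also meet early, and "the E-DMC may recommend to the Sponsor that a dose of sisunatovir be terminated".

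Section 10.3.3 (Assessment of Intensity) keeps severity and seriousness apart: an event is serious because of its outcome, not because of its intensity rating. The SAP adds no interruption rule.

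**The concern.** A set of interruption rules should never lose a trigger because an observed event gets worse. This set can. Rule 3 accepts that two unlike, related severe events in two children may be enough to interrupt. By restricting itself to nonserious events, it drops the pair once either event meets an SAE criterion. Rule 2 does not pick the pair up unless both are SAEs in one SOC.

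The pattern is foreseeable, although its rate is unknown. Hospitalized children are eligible (Section 4.1), and prolonging a hospital stay makes an event serious (Section 10.3.2). The potential drug risks in Section 2.3.1 span the hepatobiliary, gastrointestinal and cardiovascular systems. The one pediatric SAE described in Section 2.2.4, a fever judged unrelated, was serious because it prolonged hospitalization. Suppose one inpatient has severe related vomiting and another child has a severe related event of a different kind. If both are nonserious, rule 3 can apply. If the vomiting prolongs the hospital stay, no listed rule applies.

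At stake are the prespecified trigger and the E-DMC lock on restarting dosing, in a study that enrolls children from 1 day of age.

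**Working it through.** The plan gives no figure to reproduce, so this is a logical check of the five rules.

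**Fixed conditions.** Two events, one in each of two children on sisunatovir. Both are nonfatal, severe and at least possibly related, and neither is a laboratory or vital-sign finding. The judgement conditions in rules 3 and 4 are taken as met, so each entry means that the rule *can* be met.

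**When each rule can be met under these conditions.**
- Rule 1: never, because there is no death.
- Rule 2: both events serious and in the same SOC.
- Rule 3: both events nonserious, any SOC.
- Rule 4: the two events are the same or alike, whatever their seriousness.
- Rule 5: never, because neither event is a laboratory or vital-sign finding.

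**Patterns.** 2 (similar or dissimilar) × 3 (seriousness) × 2 (same or different SOC) = 12. Cells show the rules that can be met.

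| Events | Seriousness | Same SOC | Different SOC |
|---|---|---|---|
| Similar | Both nonserious | 3, 4 | 3, 4 |
| Similar | One serious | 4 | 4 |
| Similar | Both serious | 2, 4 | 4 |
| Dissimilar | Both nonserious | 3 | 3 |
| Dissimilar | One serious | none | none |
| Dissimilar | Both serious | 2 | none |

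**Count as written.** Similar pairs 6 of 6, dissimilar pairs 3 of 6, total 6 + 3 = 9 of 12. All three empty cells are dissimilar pairs with at least one serious event.

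**Count with *nonserious* deleted from rule 3.** Rule 3 can then be met in every cell: 9 + 3 = 12 of 12.

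**Boundary checks.**
- If either event is a related death, rule 1 is met by that event alone, so the gap concerns nonfatal events only.
- If the events are laboratory findings but still dissimilar, the result is unchanged, because rule 5 needs similar findings.
- If the events are mild or moderate SAEs in different SOCs, rule 3 fails on intensity with or without the word *nonserious*. The 12 of 12 therefore holds only for severe events.

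The patterns are unweighted. Section 2.2.4 reports no SAEs attributable to sisunatovir as of 20 January 2024, and the documents give no rate of related SAEs from which to derive a probability.

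**The case against.** The strongest reply is that Section 4.1.1 should not be read apart from its parent section. Section 4.1 requires randomization to stop for a safety signal of concern and leaves the restart to an E-DMC recommendation. Section 4.1.1 itself asks only for dosing *or* enrollment to be interrupted, so a randomization halt is much of what the list would deliver. That trigger is undefined, but rule 3 also rests on an undefined judgement of dose-limiting intolerance. Two related severe events, at least one of them serious, that were accepted as dose limiting would very likely count as a signal. This stands, and it makes the gap narrow. It does not remove it: Section 4.1 halts randomization, whereas the lock on restarting dosing is attached to the listed rules.

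Other safeguards also hold. Dosing can be stopped in an individual child for an AE that poses a risk (Section 7.1). SAEs must reach the sponsor within 24 hours (Section 8.4.1.1), and the sponsor may review unblinded data (Section 6.4.3). Treatment lasts 5 to 6 days (synopsis). The E-DMC charter (Section 10.1.5.1), which was not available, may set further triggers.

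The split could be deliberate: SAEs have an expedited reporting route and nonserious AEs do not, so a broad pooled rule adds most for the latter. That is an inference, as the documents give no rationale, and it would not explain why one serious and one nonserious event should meet no rule.

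A reader might infer two stronger claims. One is that the study would carry on unchecked after such a pair; Section 4.1 does not support that. The other is that the list treats SAEs more leniently throughout. It does not: rule 2 is easier to meet than rule 3 in that it counts events, needs no severe intensity and carries no tolerability judgement. Rule 4 can also catch alike severe events of any seriousness; since likeness is not defined, some same-SOC pairs may fall under it.

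**Conclusion.** The rule is wrong as written, with minor to moderate severity. On the plain text, a nonfatal, dissimilar, related severe pair in two children on sisunatovir can meet a listed rule when both events are nonserious. It meets none when one is serious, or when both are serious in different SOCs. The loss is the prespecified trigger and the E-DMC's control over restarting dosing, and that control itself gives way when a clear cause other than the study drug is found. The mandatory, E-DMC-gated randomization halt in Section 4.1 would probably catch such a case.

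The conclusion rests on reading seriousness and severity as separate, as Section 10.3.3 directs, and on rule 3's intolerance judgement being satisfied. No probability of the pattern and no actual harm are claimed. Confidence is high about the wording gap, and does not extend to a claim that children would go unprotected.

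**What to change.** In rule 3 of Section 4.1.1, delete *nonserious*, so that it opens *Severe AEs (serious or nonserious)* and otherwise stays as it is. Keep rule 2 unchanged, because it covers same-SOC SAEs of any intensity. Align the E-DMC charter if needed.

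This repairs the ordering for severe events only. Related SAEs of mild or moderate intensity in different SOCs would still meet no rule, unless they are similar laboratory or vital-sign findings that satisfy rule 5.

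The edit is one word, but the process is larger. The history of Amendment 1 (Section 10.11) classed changes to these rules as substantial, and Section 10.1.1 requires IRB/EC approval for amendments and health authority approval for substantial ones. It can be bundled with the next amendment. The operational downside is a possible extra pause for E-DMC review, limited by rule 3's intolerance condition and by the allowance to continue when a clear cause other than the study drug is found.
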